13.2.2 Examination of the pelvic veins for research protocol

Following the completion of the assessment of the pelvic organs, we will examine the pelvic veins for the presence of blood clots. The veins will be identified lateral to the uterus and followed within the broad ligament until they reach the point where they drain into internal iliac veins. The maximum diameter of the largest vein will be recorded in the transverse plane. Flow velocity studies will be performed using Doppler ultrasound with and without the Valsalva manoeuvre.

Diagnosis of pelvic vein thrombosis will be made in women with evidence of single or multiple well-defined echogenic lesions within the lumen of pelvic veins causing a partial or complete obstruction to blood flow on colour Doppler examination⁶. In all cases the diagnosis will be confirmed by a senior clinician. If the diagnosis is confirmed the thrombi will be measured in 3 orthogonal planes and the diameters will be recorded. These results will compared to the findings on subsequent follow up scans.

13.3 Procedure for women diagnosed with pelvic vein thrombosis

Women diagnosed with pelvic vein thrombi will be advised about the uncertainty regarding clinical significance of this condition. They will be offered a full thrombophilia screen on the day of diagnosis. Those with abnormal results of blood tests will be contacted immediately and referred to a consultant haematologist for review and advice regarding further investigations and management. Women with negative thrombophilia screen will be offered another scan one month later to check for the resolution of the blood clot. Those with persistent clots will be seen again three and six months later. If at any point patients are concerned about the diagnosis or have queries they will be referred for haematological consultation. Those with persistent blood clots at the six month visit will also be offered an appointment with the consultant haematologist to discuss further management.

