1.3 Protocol Details

Version 3 17th October 2014

2 Signature Page

Prevalence of pelvic vein thrombosis

3 Contents

3.1	Background and literature review	Page: 5
3.2	Aims and Objectives	Page: 7
3.3	Study design	Page: 7
3.4	Study group	Page: 7
3.5	Recruitment of participants	Page: 8
3.6	Data collection	Page: 9
3.7	Data handling	Page: 10
3.8	Study procedure	Page: 11
3.9	Statistical Plan	Page: 14
3.10	Compliance	Page: 14
3.11	Study administration	Page: 15
3.12	Publication plan	Page: 15
3.13	Indemnity statement and Incident reporting	Page: 15
3.14	Appendix	Page: 17

4 Abbreviations

COCP = combined oral contraceptive pill GDOTU = Gynaecology Diagnostics and Outpatient Treatment Unit POP = progestogen only pill VTE = venous thromboembolism DVT = deep vein thrombosis PE = pulmonary embolism TV US = transvaginal ultrasound

5 Summary of Research

Deep vein thrombosis is an important health problem. Recent studies have shown that a proportion of women attending for a gynaecological ultrasound scan have evidence of asymptomatic pelvic vein thrombosis. This is a novel observation and the clinical significance of this finding is unknown. The primary aim of our study is to establish the prevalence of asymptomatic pelvic vein thrombosis in the population of women attending gynaecological outpatient clinics. Our secondary objectives are to study the natural history of pelvic vein thrombosis and to identify factors which may contribute to their formation.

We are planning to conduct a prospective cross sectional observational study. We aim to recruit women who are referred to our gynaecological outpatient department for clinical assessment and ultrasound scans. In all women, in addition to the standard examination of pelvic organs, we will examine the pelvic veins and look for the signs of thrombosis. Those with evidence of blood clots in the pelvis will be offered a thrombophilia screen. Women with positive results will be then referred for haematological assessment. Those with negative thrombophilia screen will be followed up at one, three and six months following the initial diagnosis or until resolution is documented on the scan. Women with persistent clots after six months follow up will also be offered haematological assessment and advice. We aim to include 2574 women over 19 months.

6 Background

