10.3 Study Timetable

Recruitment will run between the 1st January 2015 to 31st August 2016.

8

Sept 2014, ver 3.

11 Data Collection

The data source will be from the history taken and ultrasound scan performed during the consultation, which is recorded onto a secure NHS database (Viewpoint). Although this is usual standard care, the clinical data will be included as part of the research study. Information about the ultrasound findings will be collected at the initial consultation and at the follow up scan appointments if there is a pelvic vein thrombus at four weeks, three months and six months by the student involved in this study ([name], EGA wing, UCLH).

The following data will be collected at the time of consultation and scan: anonymous demographic information (age, BMI, ethnicity, smoking history); obstetric history (gravida, parity, pregnancy outcome, type of delivery, uterine instrumentation in pregnancy, instrumentation of uterus outside pregnancy); gynaecological history (age of menarche, number of days of menstruation, menorrhagia, dysmenorrhea, dyschezia, breastfeeding history, use of COCP or POP, use of coils); past medical history (cancer, varicose veins, recent surgery); ultrasound findings (uterine shape/anomaly, presence of adenomyosis, presence of fibroids/mass and size, ovarian volume, adnexal mass, maximum uterine vein diameter, blood flow velocity, flow rate, presence of clot, size of clot at initial scan and then at follow up at one, three and six months); thrombophilia screening results. Please see appendix 20.3 for a full data set.

The data will be entered into a spreadsheet (Microsoft Excel version 14.0) (see appendix 20.3).

12 Data Handling and Record Keeping

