14.1 Sample Size Determination and Power

We aim to screen 2574 eligible participants over 2 years. The prevalence of this condition is unknown but our initial experience indicates that it may be around 5/1000 women and the sample size has been calculated on this proportion ⁽¹⁷⁾.

14.2 Statistical Methods:

We will perform multivariate logistic regression analysis to identify factors which may be contributing to asymptomatic pelvic vein thrombosis.

15 Compliance

15.1 Subject Compliance:

Patients who do not have a pelvic vein thrombus will not be followed up in the study. Those with a thrombus will have scheduled follow up appointments at one, three and six, months. If there is evidence of clot resolution at the first or second visit, no further follow up will be arranged. Women who fail to attend for their appointments, will be contacted by telephone and will be offered another date for the follow up visit.

15.2 Withdrawal of subjects:

Patients will have the opportunity to withdraw from the study at any point in the study period. Patients will be asked if the data collected upto the point of withdrawal can be used in the final analysis.

16 Study Administration

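### The protocol contradicts itself on who is followed up after a thrombus is found, so the group behind the natural-history outcome is undefined

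*Protocol*

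**What the plan says.** The summary (section 5) sets the objective: "Our secondary objectives are to study the natural history of pelvic vein thrombosis and to identify factors which may contribute to their formation". Follow-up of women with a thrombus is then described in four places.

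- **Section 5:** "Those with negative thrombophilia screen will be followed up at one, three and six months following the initial diagnosis", or until a scan documents resolution.
- **Section 13.3:** "They will be offered a full thrombophilia screen on the day of diagnosis". The paths then divide. For one group, "Those with abnormal results of blood tests will be contacted immediately and referred to a consultant haematologist for review". For the other, "Women with negative thrombophilia screen will be offered another scan one month later to check for the resolution of the blood clot", with further visits if the clot persists.
- **Section 11:** ultrasound findings are collected at the first consultation and at "follow up scan appointments if there is a pelvic vein thrombus at four weeks, three months and six months". No condition on the screen is given.
- **Section 15.1:** "Those with a thrombus will have scheduled follow up appointments at one, three and six, months". The only women it names as not followed are those without a thrombus.

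Section 13.2.2 also plans to compare the measurements of confirmed thrombi with later scans, without restriction by screen result.

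**The concern.** Staff working from section 13.3 would book scans for screen-negative women. Staff working from section 15.1 would book them for every woman with a thrombus. No passage says which governs, and none defines the population for the natural-history objective.

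If 13.3 is followed as written, the outcome describes a subgroup chosen on thrombophilia status but would be reported as the natural history of pelvic vein thrombosis in general. Section 13.3.1 presents that information as the first of its kind and as a basis for counselling women. An analysis plan cannot repair this afterwards, because it cannot supply scans that were never made.

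**Working it through.** **1. The passages side by side**

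| Woman with a confirmed thrombus | Sections 5 and 13.3 | Sections 11 and 15.1 |
|---|---|---|
| Screen negative | Follow-up scans | Follow-up scans |
| Screen abnormal | Haematology referral; no study scan stated | Follow-up scans |
| Screen offered but declined | No stated route | Follow-up scans |

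The two versions agree on the first row only.

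**2. Expected number of cases**

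Section 14.1 gives 2574 women and an assumed prevalence of 5 per 1000. Expected cases = 2574 x 0.005 = 12.87, about 13. The binomial 95% range is 6 to 20.

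**3. Number followed under each version**

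Sections 11 and 15.1 follow all 13. Under sections 5 and 13.3 the number depends on the share who screen positive, which the protocol does not give. Assuming that every woman is tested:

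- 10% positive: 13 x 0.9 = 11.7
- 30% positive: 13 x 0.7 = 9.1
- 50% positive: 13 x 0.5 = 6.5

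Women who decline the screen would reduce these numbers further.

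**4. Effect on a resolution proportion (all rates assumed)**

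Take 70% resolution in screen-negative women and 30% screening positive. The screen-negative group gives 70% throughout. The all-case figure depends on resolution in screen-positive women:

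- 30% resolve: 0.7 x 0.7 + 0.3 x 0.3 = 58%
- 70% resolve: 0.7 x 0.7 + 0.3 x 0.7 = 70%
- 90% resolve: 0.7 x 0.7 + 0.3 x 0.9 = 76%

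Restriction to screen-negative women can therefore overstate, match or understate the all-case figure.

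**5. Influence of one woman**

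With r of 13 resolved, losing a woman whose clot did not resolve shifts the proportion by r/12 - r/13 = r/156. Losing one whose clot resolved shifts it by (13 - r)/156. At r = 10 these are 10/156 = 6.4 points and 3/156 = 1.9 points. The largest possible shift is 12/156 = 7.7 points.

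**6. Precision**

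The exact 95% interval is 39% to 91% for 9 of 13, and 35% to 93% for 7 of 10. The estimate is imprecise under either version.

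**The case against.** The best defence is that the passages can be harmonised. Section 13.3 does not say that referred women leave the study or lose their scans, so referral could be in addition to follow-up. Equally, 15.1 could be shorthand for the 13.3 pathway. Either is possible, but the two give different groups and nothing in the text chooses between them. A restriction to screen-negative women is also defensible in itself. Section 13.3.1 says that in most reported cases diagnosis leads to anticoagulation under haematologists, and pooling treated with untreated women would not describe an untreated course. That supports stating the restriction, not leaving it unstated.

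A reader might infer more than the documents support:

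- **That no outcome is collected for referred women.** Section 13.3 states no study scan for them, but sections 11 and 15.1 would include them.
- **That the resolution rate would be too favourable.** Section 6.1 says thrombophilia raises the risk of developing venous thromboembolism; it says nothing on resolution. Referred women may also be treated, which could raise their resolution rate.
- **That the visit dates conflict as well.** The wording on later visits in 13.3 is loose, but the same paragraph refers to a six-month visit, in line with the other sections.
- **That each lost woman moves the result by about 8 points.** That is the maximum, not the usual shift.

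It also stands that only a secondary objective is affected.

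**Conclusion.** The contradiction is real and in the current text, with two sections on each side. The group behind the natural-history outcome is undefined, and under 13.3 it is selected on thrombophilia status. About 13 cases are expected if the protocol's 5 per 1000 holds. How many of them would go unfollowed depends on the share who screen positive or decline, which the documents do not give. Bias arises only if resolution or treatment differs by screen result; its direction and size cannot be determined from the documents. The primary prevalence estimate is unaffected. This is a should-fix point.

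**What to change.** Reconcile sections 5, 11, 13.3 and 15.1 into one statement of who is followed, including women who are not tested. Which clinical pathway stands is for the investigators; this review does not choose it. The analysis population should then match it:

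- **If every woman with a thrombus is followed:** use all confirmed thrombi as the natural-history denominator and record any anticoagulation. Report clot status at one, three and six months by thrombophilia result (negative, positive, not tested) and by treatment. Follow-up ends once resolution is documented, so count those women as resolved by that time; count other women without a scan as unknown.
- **If only screen-negative women are followed:** restrict the stated secondary outcome and its conclusion to them, and report how many women with a thrombus were not followed and why (abnormal screen or not tested).

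The cost is a short amendment and a few extra data items for a handful of women.

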13.3.1 Ethical Considerations

Natural history and clinical significance of incidentally diagnosed pelvic vein thrombosis is uncertain. In standard clinical practice deep vein thrombosis is typically diagnosed in symptomatic women who are routinely offered treatment with anticoagulants. Although this policy is appropriate for women with leg thrombosis there is some evidence that pelvic vein thrombosis follows more benign clinical course with a majority of clots resolving spontaneously without causing any clinical symptoms. Symptomatic and asymptomatic deep venous thrombosis can often lead to long-term venous dysfunction with the development of post-thrombotic syndrome. Animal studies have demonstrated that thrombi forming under reduced flow conditions are less likely to resolve spontaneously which can lead to fibrosis-mediated remodeling of the vessel wall ⁽¹⁸⁾. Deatrick et al ⁽¹⁹⁾ conveyed that even if there is resolution of the thrombus, the vein wall is often thicker, reflecting scarring, chronic thrombus adherence and fibrosis. These are often seen as phelboliths, which are calcified foci within a vein wall. They are visible on plain radiograph, ultrasound and CT as hyperechoic lesions in 42-45% of women ^(15, 16), implying that the prevalence for asymptomatic venous thrombosis may be higher than previously thought.

Success of treatment of pelvic vein thrombosis is uncertain and our initial data shows that thrombi may recur after the treatment is stopped, with no evidence of embolism. In these cases women tend to be offered life-long anticoagulation which is associated with significant physical and psychological morbidity. In the absence of any data on the natural history of pelvic vein thrombosis counselling of women is very difficult and arbitrary. Our study will provide for the first time information about natural history of pelvic vein thrombosis which is the first and essential step in the process of developing rational, evidence based approach to difficult clinical problems. Diagnosis of pelvic vein thrombosis in the majority of reported cases leads to treatment with anticoagulation under the guidance of haematologists. Although anticoagulation with low molecular weight heparin or warfarin is a recognized and safe treatment it can be associated with side effects, particularly when given over a prolonged period of time.

Risks and Benefits:

The risk of overtreatment is described in 13.3.1. The main benefit for participants is that screening for asymptomatic pelvic vein thrombosis may help to understand this condition better and to provide them and other women with evidence based treatment to this rare and complex problem.

14 Statistical Plan

This study will follow the Strengthening the Reporting of Observational Studies in Epidemiology (STROBE) methodology for observational studies¹⁴. It comprises of a checklist of 22 items to ensure accurate data collection, analysis and reporting (see appendix 20.4).

14.1 Sample Size Determination and Power

We aim to screen 2574 eligible participants over 2 years. The prevalence of this condition is unknown but our initial experience indicates that it may be around 5/1000 women and the sample size has been calculated on this proportion ⁽¹⁷⁾.

14.2 Statistical Methods:

We will perform multivariate logistic regression analysis to identify factors which may be contributing to asymptomatic pelvic vein thrombosis.

15 Compliance

15.1 Subject Compliance:

Patients who do not have a pelvic vein thrombus will not be followed up in the study. Those with a thrombus will have scheduled follow up appointments at one, three and six, months. If there is evidence of clot resolution at the first or second visit, no further follow up will be arranged. Women who fail to attend for their appointments, will be contacted by telephone and will be offered another date for the follow up visit.

15.2 Withdrawal of subjects:

Patients will have the opportunity to withdraw from the study at any point in the study period. Patients will be asked if the data collected upto the point of withdrawal can be used in the final analysis.

16 Study Administration

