In recent years an increasing number of women are having transvaginal ultrasound scans for a wide range of gynaecological indications. The pelvic veins are often examined in women presenting with pelvic pain to rule out pelvic congestion syndrome. However, there is a paucity of data on the diagnosis and prevalence of incidental pelvic vein thrombosis in women. Recently we have published a first report in the literature describing ultrasound diagnosis of pelvic vein thrombosis in six asymptomatic non-pregnant women. Our data showed that pelvic vein thrombosis is not as rare as previously thought and that majority of women had identifiable predisposing factors for development of blood clots. Although the diagnosis of pelvic vein

6

thrombosis on ultrasound is relatively simple the natural history, clinical significance and optimum management strategy are unknown.

7 Aims and Objectives

The primary aim of the study is to determine the prevalence of pelvic vein thrombosis in women attending gynaecology outpatient clinic. The secondary outcomes are: natural history and identification of factors contributing to clot formation.

8 Study Design

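### About 13 cases are expected at the protocol's own planning figures, too few for the multivariable logistic regression in Section 14.2 to identify contributing factors reliably

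*Protocol*

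**What the plan says.** Section 14.1 sets the size of the study: "We aim to screen 2574 eligible participants over 2 years". On the basis for that number it says that "our initial experience indicates that it may be around 5/1000 women and the sample size has been calculated on this proportion". No other quantity is tied to the sample size.

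Section 14.2 consists of one sentence, and it names the only analysis method in the Protocol: "We will perform multivariate logistic regression analysis to identify factors which may be contributing to asymptomatic pelvic vein thrombosis". It gives no covariate list, no limit on the number of terms, no estimator and no selection rule.

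Section 7 gives this analysis its status: "The secondary outcomes are: natural history and identification of factors contributing to clot formation".

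Section 11 lists the data to be collected on each woman under demographic, obstetric, gynaecological, medical and ultrasound headings. It does not say which items are model covariates.

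**The concern.** The number of women with a clot, not the 2574 scanned, limits what a logistic model can estimate. Sections 14.1 and 14.2 stand next to each other, and the case count implied by the one is never related to the model promised in the other.

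With few cases, an uncommon exposure may be absent from every case. The maximum-likelihood odds ratio for it is then zero or infinite and the fit does not converge properly. Fits that do converge can show extreme odds ratios where no association exists. By the Protocol's account, data on this condition are scarce, so factors reported from this study could carry weight in counselling. At stake is the content of a named secondary objective.

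**Working it through.** **Inputs from the Protocol.** N = 2574 and prevalence P = 0.005 (Section 14.1); candidate characteristics (Section 11). The documents give no exposure prevalences, so those used below are assumptions, shown over a range. Factors are taken as independent of each other and of the outcome.

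**1. The planned N.** The single-proportion formula is n = z²P(1−P)/d². The Protocol gives neither d nor the confidence level, so 2574 can only be solved backwards. At 95%, d = √(1.96² × 0.005 × 0.995 / 2574) ≈ 0.0027. Nothing in this calculation concerns the regression.

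**2. Expected cases.** 2574 × 0.005 = 12.87, about 13. The binomial 95% range, with the rate fixed at 0.005, is 6 to 20.

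**3. Candidate factors.** Demographic 4, obstetric 6, gynaecological 8 (the two pill types counted as one), medical 3, ultrasound 8: 4 + 6 + 8 + 3 + 8 = 29. Clot data are left out because they are the outcome. Thrombophilia results are left out because Section 13.3 offers the screen only to women with a clot.

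**4. Events per factor (12.87 / k).**

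| Factors in model | Events per factor |
|---|---|
| 1 | 12.9 |
| 2 | 6.4 |
| 5 | 2.6 |
| 10 | 1.3 |
| 29 | 0.44 |

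**5. Chance that no case is exposed.** For an exposure of prevalence q under no association this is (1 − 0.005q)^2574: 53% at q = 5%, 28% at 10%, 8% at 20% and 2% at 30%.

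For two factors, the chance that at least one has no exposed case is the sum of the two single chances minus the chance that both are empty:
- 10% and 20%: 0.276 + 0.076 − 0.027 = 0.325. Simulated fits separated in about 32%.
- Both 30%: 0.021 + 0.021 − 0.001 = 0.041. Simulated fits gave about 4% to 5%.

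For five factors, by the same inclusion–exclusion sum or by simulation:
- three binary at 10%, 20% and 40% plus two continuous: 34% separated in simulation;
- five binary at 5%, 10%, 10%, 20% and 20%: 76%;
- five binary all at 30%: about 9%.

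**6. Most of the list entered.** Simulated null data, N = 2574, 18 binary and 11 continuous factors:
- Binary prevalences of 5% to 50%: 95% of 150 data sets separated.
- Every binary factor at 30%: 27% of 100 data sets separated. Of the 73 that could be fitted, 86% had at least one odds ratio above 3 or below 1/3, and 67% had at least one p < 0.05.

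The 67% is not evidence of inflated tests. Twenty-nine independent tests at 5% would give 1 − 0.95^29 = 77%. The false positives come from the number of factors examined, and the extreme odds ratios from the few cases.

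**7. Power for one factor.** With 13 cases, a single unadjusted binary exposure of 5% to 50% prevalence needs an odds ratio of roughly 5 to 8 for 80% power.

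**8. Primary aim.** Thirteen cases in 2574 give an exact 95% interval of about 2.7 to 8.6 per 1000. The regression does not touch it.

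**The case against.** Section 14.2 says very little, and a reader might infer more from it than it contains.

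- **All 29 characteristics enter the model.** Section 11 is a data-collection list. Some items describe the patient, and vein diameter and flow may be consequences of a clot. The 0.44 events per factor and the 95% failure rate therefore describe a model that nobody has specified.
- **Estimation is unpenalised and selection is stepwise.** Neither is stated. A Firth-penalised model would satisfy the wording, and covariates, estimator and selection can properly be left to a statistical analysis plan.
- **Failure is certain.** It is not. Two factors at 30% separate in about 4% to 5% of fits, and five at 30% in about 9%.
- **The case count is a guess.** Section 14.1 calls the prevalence unknown. At an assumed 1% there would be about 26 cases (2574 × 0.01) and at 2% about 51, enough for a modest model.
- **Reporting is already covered.** The STROBE checklist in Appendix 20.4 asks for unadjusted estimates, precision and a discussion of multiplicity.

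The first three points stand and limit the finding. The fourth is a reason to let the model grow with the observed cases, not a reason to plan as if they were there. The fifth covers reporting only. An analysis plan can shorten the covariate list, but it cannot add events: any multivariable model has at least two factors, and so at most about 6.4 expected events per factor.

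**Conclusion.** The concern holds as a should-fix. At 2574 women and 5 per 1000, the multivariable regression promised in Section 14.2 has about 13 cases (6 to 20) and cannot be relied on to identify contributing factors. With a short list, the risk of separation is roughly 5% to 32% for two factors. For five factors that include an uncommon exposure it is about 34% to 76%, falling to about 9% if all five are common. If most of the Section 11 list were entered, failure would be very likely unless nearly all exposures were common. Where a fit does converge, extreme odds ratios can appear under no association.

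These rates rest on assumed exposure prevalences, independent factors, ordinary maximum likelihood and the planning prevalence.

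A reader might infer that the secondary objective is bound to give a wrong answer, or that the study as a whole is undermined. The documents support neither. Separation usually shows as unbounded or very wide intervals that an analyst would notice. The sample size is tied to prevalence, and that estimate is untouched.

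**What to change.** Revise Section 14.2 so that it:

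1. states the expected number of cases (about 13, range 6 to 20 at 5 per 1000);
2. labels the factor analysis exploratory;
3. reports each factor univariably with an exact 95% confidence interval;
4. limits any multivariable analysis to one Firth-penalised logistic model with one or two factors chosen by the investigators in advance, profile-likelihood intervals and no data-driven selection;
5. says that independent risk factors cannot be established at this case count;
6. allows a larger model only if substantially more cases are observed.

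The limit of one or two factors reflects a rule of thumb of 5 to 10 events per parameter, which is an assumption and not a figure from the Protocol: 12.87 / 10 ≈ 1.3 and 12.87 / 5 ≈ 2.6. Firth's penalty keeps estimates finite but adds no information, so the intervals will still be wide.

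The change is to wording only and needs no more participants. The cost is a more modest claim for the secondary objective.
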